The secondary outcomes are the differences in the change between the intervention and control groups in the PGSI scale at 6 months, in neuropsychiatric symptoms (NPSs) measured by the Neuropsychiatric Inventory (NPI-NH) (45), quality of life measured by the Quality of Life in Late-Stage Dementia scale (QUALID) (46, 47), distress perceived by the next of kin measured by the Relative Stress Scale (48), rejection of care measured by the Minimum Data Set (49), activities of daily living assessed with the Physical Self-Maintenance Scale (PSMS) (50), prescribed medications collected from the medical records (51), frailty measured with the Clinical Frailty Scale (CFS) (52), institutionalization at three and six months, and pain and discomfort assessed by the EQ-5D questionnaire (53) at six months. All these questionnaires have been proven to have acceptable validity and reliability. The trial will also collect data to be used as covariates in the RCT and to describe the sample of participants. These data will be collected with questionnaires answered by the staff in home care services:

- a) Age (covariate in the RCT), sex, level of education and employment status, marital status, living conditions (living alone or with someone)
- b) Hours a week and type of home care service
- c) Relation to next of kin (e.g., next of kin and how often they meet)
- d) Physical health measured with the General Medical Health Rating Scale (GMHR) (54)
- e) Cognitive function assessed by the Clinical Dementia Rating Scale (CDR) (55) (covariate in the RCT).

Table 3 Overview of the data collection in WP2 with primary and secondary outcome measures

Data collected	Interviewers	Respondents	Baseline	3 months	6 months
Characteristics of the participants					
Age ^a , gender, level of education and employment status, marital status and living conditions	Data assessors from AFS ^b	Staff members in the home care services	X		
Hours a week and type of service from the home care service	Data assessors from AFS	Staff members in the home care services	X		
Number of visits per day from the home care service	Data assessors from AFS	Staff members in the home care services	X		
Relation to next of kin (e.g., next of kin and how often they meet)	Data assessors from AFS	Staff members in the home care services	X		
Diseases (known diagnosis)	Data assessors from AFS	Staff members in the home care services	X		

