The data will be presented as frequencies and percentages for categorical and means (standard deviations) for the continuous variables. The normality of continuous variables will be assessed graphically. If necessary, skewed data will be transformed. Differences in the changes in outcomes between the intervention group and the control group will be assessed by a linear mixed model with fixed effects for time component and group and the interaction between the two. The analysis will be performed as an intention-to-treat analysis. A significant interaction will imply the differences in change between the groups. Random effects for patients nested within municipalities and slopes (if significant) will be included into the model. Individual time point contrasts will be derived within each group at each time point with the corresponding 95% confidence intervals and p-values. Linear mixed model correctly adjusts estimates for intra-cluster correlations as well as for intra-individual correlations due to repeated measurements in time. The model also handles unbalanced data by allowing inclusion of all available information, also from dropouts. The analyses for primary and secondary outcomes will be adjusted for baseline PGSI-scores, baseline severity of dementia (Clinical Dementia Rating), and age of the participants.

For RQ2 the dependent variables will be the changes from baseline in primary or secondary outcomes that are statistically significant after the implementation of TIME. Independent variables will be participants characteristics from the RCT, and organizational data (staff characteristics and organizational data) assessed in the process evaluation study in WP3.

Data analysis of qualitative data for RQ3

For the analysis, thematic content analysis will be used. Thematic content analysis is a method with the purpose to identify, analyse, and report patterns and themes in qualitative data (59, 60). The aim is to provide a systematic description of both the manifest and latent content of the data, and in the

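### The only between-group model in the protocol is a linear mixed model with a time-by-group interaction; applied to institutionalisation, naturally read as yes/no and zero at baseline, it gives wrong error rates

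*Protocol*

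**What the plan says.** The Protocol section on baseline data and outcome measures opens its list of secondary outcomes with "The secondary outcomes are the differences in the change between the intervention and control groups in the PGSI scale at 6 months". The same sentence goes on to "institutionalization at three and six months, and pain and discomfort assessed by the EQ-5D questionnaire (53) at six months". Institutionalisation is therefore listed among outcomes framed as a difference in change. It has no row in Table 3 and is not defined further.

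The section on data processing and statistical analysis for RQ1 and RQ2 gives the method: "Differences in the changes in outcomes between the intervention group and the control group will be assessed by a linear mixed model". The decision rule is "A significant interaction will imply the differences in change between the groups". The random part is "Random effects for patients nested within municipalities and slopes (if significant) will be included into the model". The scope of the adjustment is "The analyses for primary and secondary outcomes will be adjusted for baseline PGSI-scores, baseline severity of dementia (Clinical Dementia Rating), and age of the participants".

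No logistic, marginal, ordinal, count or time-to-event model appears. Categorical variables are mentioned only for description, as frequencies and percentages.

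**The concern.** The Abstract describes the participants as living in the community, and the inclusion criteria count a high risk of acute institutionalisation as a ground for entry. On that reading the outcome has no variance at baseline and variance p(1-p) at 3 and 6 months. The stated model, with one constant residual variance, averages over these. Municipality differences also arise only after baseline, so a municipality intercept alone does not carry them into the time-by-group interaction. The rule for transforming skewed data cannot repair a two-valued variable.

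Institutionalisation is one of the events the trial hopes to prevent, so a wrong p-value here matters to readers. It can also spread. RQ2 takes as dependent variables those primary or secondary outcomes that turn out statistically significant, so a false positive would pass into a second analysis.

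**Working it through.** The protocol gives no figure for this outcome, so there is none to reproduce.

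**Inputs from the protocol:** 30 municipalities with about 5 patients each; the model, the interaction test and the random-effects rule quoted above; ICC 0.10, which the sample-size section assumes for the PGSI and which is borrowed here.

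**Assumptions:** a yes/no outcome, zero for all at baseline; absorbing (once institutionalised, always counted so) unless stated; no true effect; a two-sided 5% test; event rates as shown.

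**Closed form, random intercepts only, rates 15% and 25%, ICC 0**
- Variances at 0, 3 and 6 months: 0; 0.15 × 0.85 = 0.1275; 0.25 × 0.75 = 0.1875. Sum 0.315.
- Covariance of the 3- and 6-month values: 0.15 - 0.15 × 0.25 = 0.1125.
- Variance of the three-visit sum: 0.315 + 2 × 0.1125 = 0.540.
- Pooled within-patient variance: (0.315 - 0.540/3)/2 = 0.0675.
- Model variance of any change from baseline: 2 × 0.0675 = 0.135.
- 6 months: true variance 0.1875. SE ratio √(0.135/0.1875) = 0.849. Type I error 2 × {1 - Φ(1.96 × 0.849)} = 9.6%.
- 3 months: true variance 0.1275. SE ratio √(0.135/0.1275) = 1.029. Type I error 4.4%.

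**With ICC 0.10:** the design effect is 1 + (5 - 1) × 0.10 = 1.4. It raises the true variances to 0.2625 and 0.1785 and leaves the model's 0.135 about unchanged. The SE ratios become 0.717 and 0.870, and the type I errors about 16% at 6 months and 8.8% at 3 months.

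**Effect of random slopes.** With a patient slope variance d on linear time (0, 1, 2) and residual variance s², the model variance of change is d + 2s² at 3 months and 4d + 2s² at 6 months. The true variances have ratio 0.1875/0.1275 = 1.47. If d is large relative to s², the model ratio is well above that, which makes the 3-month variance too small and the 6-month variance too large. In refits of 1,000 null trials per setting the patient slope was significant in every run, so the protocol's rule would keep it.

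**Simulated rejection rates, absorbing outcome**

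| Model | Rates at 3/6 months | ICC | 3-month contrast | 6-month contrast | Joint interaction |
|---|---|---|---|---|---|
| Intercepts only | 5/10% to 30/50% | 0 | 2.6-5.3% | 7.4-10.1% | 5.0-5.6% |
| Intercepts only | 5/10% to 30/50% | 0.10 | 5.7-10.0% | 13.3-17.1% | 10.2-10.8% |
| With slopes | 15/25% | 0 | about 8-9% | about 3% | about 10% |
| With slopes | 15/25% | 0.10 | about 13-17% | about 5-8% | about 13-16% |

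The intercept-only rows use 20,000 runs per setting. A direct mixed-model fit at 20/35% and ICC 0.10 (446 fits) gave 7.4% at 3 months and 15.2% at 6 months.

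**Benchmark.** A t test on the municipality proportions at 3 or 6 months, with no baseline row, rejected in 3.9-5.1% at ICC 0.10 over the same range of rates as the intercept-only rows.

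**The case against.** The strongest objection is that intercepts alone are not the stated model. Slopes enter if significant, and they bring the 6-month error close to nominal. This stands. A reader might infer that the plan yields a false-positive rate of up to 17% at 6 months, but under its own slope rule it does not. What remains is error at 3 months and in the joint interaction test, and that test is the stated decision rule.

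A reader might also infer that clustering is ignored for this outcome. That holds only if slopes stay at patient level. The protocol does not restrict them so, and a municipality slope does carry clustering into the interaction. One set of fits at ICC 0.10 put the 6-month error at 4% with municipality slopes.

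The premises are inferred: nowhere is institutionalisation called yes/no, absorbing or zero at baseline. If only the two follow-up times were modelled, the zero-variance baseline would not arise. If the state can reverse and the ICC is 0, the intercept-only 3-month test is too cautious (0.5-1.8%). These points limit the size of the error, but they do not make a normal model with a baseline row suitable.

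It can be said that the model sentence follows remarks on continuous variables, that the sentence naming secondary outcomes concerns covariates, and that a separate SAP may name another method. But the protocol assigns its one model to outcomes without exception, and the point concerns what it states.

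Finally, one might extend the criticism to "prescribed medications collected from the medical records" and to rejection of care. The documents do not support that: both are measured at baseline, and the protocol does not say how either is scored.

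**Conclusion.** The concern holds in a limited form. As written, the protocol applies a constant-variance linear mixed model to an outcome that is, on its natural reading, binary and zero for all at baseline. The resulting tests do not hold their 5% level. With the slopes that the rule would admit, at 15% and 25% event rates, the excess lies in the 3-month contrast and the joint test, at roughly 8-10% with ICC 0 and 13-17% with ICC 0.10. With intercepts only it lies mainly at 6 months.

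The size and place of the error depend on event rates, ICC, reversibility and the random-effects structure, none of which the protocol fixes for this outcome. The simulations leave out attrition and the covariates. One secondary outcome is affected, and nothing here touches the primary PGSI analysis. The point is minor to moderate: it should be corrected, but it does not threaten the trial's main conclusion.

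**What to change.** In the analysis section, restrict the linear mixed model to the continuous scales. For institutionalisation, compare the groups at 3 and at 6 months with a method for clustered binary data and no baseline time point. This can be a mixed logistic model with a municipality random effect, or a comparison of municipality-level proportions. Of the two, only the municipality-level comparison was checked above. Take this outcome out of the difference-in-change wording, state how it is coded (status at the visit, or any event up to then), and add it to Table 3.

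The cost is a few sentences and standard software. No new measurements are needed beyond the 3- and 6-month status already planned. The change should be made before outcome data are analysed.

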Specially trained nurses (data assessors) from the project's research centre who are not affiliated with the municipalities will, together with staff members in the home care services, assess patients' baseline characteristics before randomisation. These data assessors will after randomisation be blinded to the randomisation result. They will assess the effect of the intervention via telephone by interviewing the participants, the next of kin and the staff members who know the patient best, at three months and six months after baseline assessments. All assessors are nurses with substantial experience and formal training on the use of the assessment scales. They will attend a one-day course on the use of the assessments scales before start of the trial. A description of the questionnaires, including data assessors, respondents and the time point(s) at which they are administered, is provided in Table 1.

Baseline data and primary and secondary outcome measures

The primary outcome of the trial is the difference in the change between the intervention and control groups in individual goal achievement to resolve or alleviate the challenges regarding crises between baseline and three months using the PGSI (scale of 1–10) (34). We chose this primary outcome because there is a need for a targeted outcome that comprises the variability in a heterogeneous population. It is very unlikely that a participant would be harmed due to participation in the RCT; therefore, it is not deemed necessary to have a harm outcome in the study. In the RCT, no new experimental treatments for the patients will be introduced, and care and all treatment actions will rely on recommended national care and treatment guidelines.

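### Entered as main effects, dementia severity and age give essentially no adjustment of the group-by-time interaction that the protocol tests

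*Protocol*

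**What the plan says.** The section on data processing and statistical analysis for RQ1 and RQ2 of the protocol specifies a "linear mixed model with fixed effects for time component and group and the interaction between the two". The test is then fixed: "A significant interaction will imply the differences in change between the groups". On random effects it says "Random effects for patients nested within municipalities and slopes (if significant) will be included into the model", and on incomplete follow-up "The model also handles unbalanced data by allowing inclusion of all available information, also from dropouts".

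The same paragraph says that the primary and secondary analyses will be "adjusted for baseline PGSI-scores, baseline severity of dementia (Clinical Dementia Rating), and age of the participants". The section on baseline data and outcome measures also marks age and CDR as covariates for the trial, and Table 3 shows both collected at baseline only. No interaction other than group by time is named anywhere. The text does not say which visits are responses, or whether the adjusters enter as main effects or by visit.

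The primary outcome is the between-group difference in PGSI change from baseline to three months.

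**The concern.** The tested effect is a difference in within-patient change. A covariate that is constant within a patient and enters as a main effect raises or lowers that patient's fitted value equally at every visit, so it drops out of the change. On the plain reading of the stated terms, CDR and age therefore sit in the model without adjusting the effect of interest.

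The intention to adjust is explicit and repeated. The Randomisation section describes random assignment of municipalities and mentions no stratification or balancing, so covariate adjustment is the only stated protection against chance imbalance across 30 clusters. At stake are that protection, the precision that adjustment is meant to bring, and the accuracy of calling the primary result adjusted.

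**Working it through.** The protocol gives no figure for what the adjustment should achieve, so there is none to reproduce.

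**1. Which visits are responses?**
- With baseline, month 3 and month 6 as responses, the group-by-time term at month 3 is the difference in change from baseline. This matches the primary outcome.
- With months 3 and 6 only, group by time is the difference in change from month 3 to month 6. This does not match it.
- The same adjustment is stated for the secondary outcomes, but the only baseline score listed is PGSI. Without their own baseline as a covariate, their differences in change can come from the stated model only if baseline is a response.

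**2. Algebra.** Let b be the fitted slope for CDR. With complete data, the fitted mean for arm g at visit t is the raw mean M(g,t) minus b × C(g), where C(g) is the arm's mean CDR, up to a common constant. C(g) does not depend on t. The difference in change is

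[M(1,3) − bC(1)] − [M(1,0) − bC(1)] − {[M(0,3) − bC(0)] − [M(0,0) − bC(0)]} = [M(1,3) − M(1,0)] − [M(0,3) − M(0,0)].

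b has gone. The same holds for age and for a baseline-PGSI main effect.

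**3. Numerical check.** 200 simulated trials per row: 30 municipalities of 5, three visits, generalised least squares with fixed variance components including a patient slope. The true effect is 2.0. For illustration, imbalances of 0.4 SD in CDR and 0.2 SD in age were built in. Entries are the mean 3-month interaction.

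| Data | No covariates | CDR, age as main effects | CDR, age by visit | Mean (max) shift from main effects | Mean shift from by-visit terms |
|---|---|---|---|---|---|
| Complete | 1.694 | 1.694 | 1.985 | 0 (1.4e-14) | 0.299 |
| About 25% random dropout | 1.744 | 1.745 | 1.977 | 0.048 (0.158) | 0.258 |
| Dropout depending on CDR | 1.759 | 1.723 | 1.949 | 0.063 (0.234) | 0.226 |

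On complete data the main effects also left the standard error unchanged (0.4705). The by-visit terms gave 0.4872, the price of correcting a deliberately imbalanced sample with the variance components held fixed.

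A REML fit to one complete data set gave 2.942 (SE 0.450) both without and with the main effects, and 3.281 (SE 0.462) with by-visit terms. With 27% dropout the three estimates were 3.107, 2.990 and 3.208. One data set shows only whether the estimate moves, not which value is nearer the truth.

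Further simulated trials used SD of change 2.83, ICC of change 0.10 and a CDR effect of -0.3 SD. With about 25% dropout, main effects moved the estimate by about 0.02 on average and CDR-by-visit terms by 0.11 to 0.19. The slope of the unadjusted estimate on the CDR imbalance was about -0.85 to -0.9, and about 0 with CDR by visit.

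For contrast, with months 3 and 6 as the only responses and baseline as a covariate, plain CDR and age terms moved the 3-month group contrast by 0.33 to 0.41 in the trials with built-in imbalance.

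**4. Size.** From the sample size section: SD of change 2.83, target 2 points, 30 clusters of about 5. Assumed: CDR ICC 0.05 and a correlation r of CDR with change.
- SD of the imbalance between arms, in CDR SD units: sqrt(2 × (1 + 4 × 0.05) / 75) = sqrt(0.032) = 0.18.
- Typical absolute imbalance: 0.18 × sqrt(2/π) = 0.14.
- P(imbalance beyond ±0.3 SD) = 0.094.
- Error in points = |r| × 2.83 × imbalance.

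| Assumed r | Per SD of imbalance | Typical (0.143 SD) | 0.3 SD | Residual SD factor, sqrt(1 − r²) |
|---|---|---|---|---|
| -0.1 | 0.28 | 0.04 | 0.08 | 0.995 |
| -0.3 | 0.85 | 0.12 | 0.25 | 0.954 |
| -0.5 | 1.42 | 0.20 | 0.42 | 0.866 |

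At r = -0.3, 0.12 points is 6% and 0.25 points 13% of the 2-point target. With 150 × 0.75 = 112.5 completers and a design effect of 1.4, the standard error is about 2.83 × sqrt(2 × 1.4 / 56.25) = 0.63, so 0.25 points is about 0.4 standard errors.

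**The case against.** Two premises are read from the text rather than stated in it. The protocol does not say that the adjusters are main effects only, and an analysis plan that is not shown could add by-visit terms. Nor does it say that baseline is a response, and listing baseline PGSI as an adjuster points the other way. Both remarks are fair, but neither removes the point. The protocol itself names the fixed effects, the test and the covariates, and on their plain reading these parts do not work together. If baseline is only a covariate, CDR and age do adjust the 3-month contrast, but the stated interaction test then no longer measures change from baseline. The paragraph needs correcting either way.

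A reader might infer that the covariates cannot adjust at all, so that the reported effect would be strictly unadjusted. The documents do not support that. The protocol expects 25% attrition and keeps dropouts in the model, and the main effects then move the estimate a little. The shift is small and is not a correction for imbalance in change, but it is not zero.

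A reader might also infer bias. Baseline is assessed before randomisation, so an imbalance in baseline CDR between the randomised arms arises by chance. Averaged over randomisations it causes no bias, and the standard error already reflects it.

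Finally, the stakes are limited: a 0.3 SD imbalance is exceeded in only about 9% of randomisations, and the correlation of CDR with change is nowhere in the protocol. That stands, and it sets the weight of the point.

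**Conclusion.** The point holds in a limited form. If CDR and age enter as main effects beside a baseline response, which is the natural reading but not an express statement, they cancel from the tested difference in change. The cancellation is exact with complete data. With the expected attrition it is near-complete, with an average shift of about 0.02 to 0.06 points. The stated adjustment then gives essentially no correction for chance imbalance and almost none of the intended precision.

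The loss is one of conditional accuracy and precision, not validity, and it is modest. At an assumed correlation of -0.3 and a CDR ICC of 0.05, a typical imbalance gives about 0.12 points of error, a 0.3 SD imbalance gives about 0.25 points, and about 5% of the residual SD is forgone. The remedy is cheap and the present wording would misdescribe the result, so it should be corrected before analysis.

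**What to change.** State which visits are responses, then choose one of two forms:

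- **(a)** Keep baseline as a response and add CDR × visit and age × visit. The tested term remains group by time at month 3.
- **(b)** Model months 3 and 6 only, with the outcome's own baseline value, CDR and age as covariates, and test the 3-month group contrast instead of the group-by-time interaction. For secondary outcomes, the own-baseline value replaces or joins baseline PGSI.

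The cost is one or two sentences and no new data. Form (a) adds 2 covariates × 2 follow-up visits = 4 fixed effects if CDR enters as a score, and more if it is categorical. Form (b) needs no by-visit terms for the covariates, but patients without any follow-up visit contribute no response rows, and the plan should say so.

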Design/Methods: This is a participatory action research design (PAR) in a six-month cluster randomized controlled trial (RCT). The trial will be conducted in 30 municipalities including 150 frail community-dwelling participants receiving homecare services judged by the services to have imminent crises. Each municipality will be defined as a cluster and will be randomized to receive either the locally adapted TIME intervention (the intervention group) or care as usual (the control group). TIME is a manual-based, multicomponent programme that will include a rigorous assessment of the crises, one or more interdisciplinary case conferences and the testing and evaluation of customised treatment measures. Primary outcome: Difference in change between intervention and control group in individual goal achievement to resolve or reduce the challenges of the crises, between baseline and 3 months using the PRACTIC Goal Setting Interview (PGSI), which is inspired by the Bangor Goal Setting Interview (BGSi scale of 1–10). Secondary outcomes: Difference in change in the PGSI scale at 6 months, and in neuropsychiatric symptoms (NPS), quality of life, distress

perceived by professional careers and next of kin, and institutionalization at 3 and 6 months. For the exploration of the factors associated with the effect of the intervention we will use multiple level regression analysis of the data from the RCT. To explore the experiences of the users of home care services with the intervention we will use qualitative in-depth interviews of dyads with 15 patients and next of kin who participated in the RCT.

Trial registration: ClinicalTrials.gov identifier, ID: NCT05651659. Registered 15.12.22.

Keywords: frailty, crises, home care services, community-dwelling people, behavioural and psychological symptoms of dementia (BPSD), psychosocial interventions, case conferences, participatory action research (PAR), randomized controlled trial (RCT), PRACTIC Goal Setting Interview (PGSI)

Protocol

Background

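### The analysis section takes an interaction with no stated time point as evidence of a group difference, so it does not isolate the 3-month PGSI comparison that is primary

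*Protocol*

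**What the plan says.** The Abstract defines the primary outcome as the between-group difference in change in "individual goal achievement to resolve or reduce the challenges of the crises, between baseline and 3 months". The section *Baseline data and primary and secondary outcome measures* repeats this: the aim is "to resolve or alleviate the challenges regarding crises between baseline and three months using the PGSI". The sample size section applies its attrition allowance to the primary outcome at three months. The later time point is clearly secondary: "The secondary outcomes are the differences in the change between the intervention and control groups in the PGSI scale at 6 months". Table 3 shows PGSI collected at baseline, 3 months and 6 months.

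The section *Data processing and statistical analysis of quantitative data for RQ1 and RQ2* gives one model form for all outcomes: "Differences in the changes in outcomes between the intervention group and the control group will be assessed by a linear mixed model". Its fixed part consists of time, group and their interaction. It then says "A significant interaction will imply the differences in change between the groups". On random effects: "Random effects for patients nested within municipalities and slopes (if significant) will be included into the model". On time points: "Individual time point contrasts will be derived within each group at each time point with the corresponding 95% confidence intervals and p-values". On missing visits: "The model also handles unbalanced data by allowing inclusion of all available information, also from dropouts". It does not say whether time is categorical or linear, or which visits enter the PGSI model.

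**The concern.** The outcome sections fix one contrast at one visit. The analysis section offers two kinds of result: an interaction tied to no visit, and visit-specific contrasts that do not compare the groups. Neither is, as written, the between-group difference in change at 3 months.

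If the model holds all three PGSI visits, the interaction can be tested in two usual ways. With categorical time, the overall test has 2 degrees of freedom and asks whether the groups differ at 3 months or 6 months. With linear time, it asks whether the 6-month slopes differ. Under either, a secondary 6-month effect can produce significance with no 3-month effect. Under the second, a 3-month effect that fades can be missed. The authors would also be left to choose between these tests when the results are in hand.

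**Working it through.** **Which visits enter.** Three features point to all visits: random slopes, the reference to repeated measurements in time, and the use of all available information. With baseline and 3 months only, a patient-level random slope could not be separated from residual error in the usual model. This is inference; the text does not settle it.

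**Inputs from the sample size section.** Difference 2; SD of change 2.83 (variance about 8); ICC 0.10; 30 municipalities of about 5; 25% lost by 3 months; 150 patients, taken as 75 per arm.

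**The plan's own figure.** Assuming two-sided 5%, n per arm = 2 × (1.96 + 0.84)² × 2.83² / 2² = 31.4, so 32. Design effect 1 + (5 − 1) × 0.10 = 1.4 gives 45. Attrition gives 45 / 0.75 = 60 per arm, 120 in total. The stated figure of about 150 is therefore not reproduced. It exceeds the need, so it does not weaken this point.

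**The 3-month contrast at 150.** After attrition there are 75 × 0.75 = 56.25 per arm, or 5 × 0.75 = 3.75 per municipality. The design effect is 1 + (3.75 − 1) × 0.10 = 1.275, and the effective number is 56.25 / 1.275 = 44.1 per arm. SE = 2.83 × √(2 / 44.1) = 0.603, and 2 / 0.603 = 3.32. Power is 89% (t, 28 df) to 91% (normal).

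**Three-visit model.** I used generalised least squares with a random patient intercept, variances multiplied by 1.275, t or F references on 28 df, and no covariate adjustment. Assumed, because the Protocol gives no figures: within-patient correlation 0.3, 0.5 or 0.7; further loss by 6 months of 0, 11 or 25%; and, in the first table, no random slopes, so that the 6-month change also has SD 2.83.

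*Joint test.* The noncentrality is λ = (z₃² − 2r·z₃·z₆ + z₆²) / (1 − r²), where z is the true effect divided by its SE and r is the correlation of the two estimates. At correlation 0.5 and 11% further loss, the SEs are 0.583 and 0.609 and r is about 0.45. For effects (0, 2): λ = (2 / 0.609)² / (1 − 0.45²) = 10.79 / 0.80 = 13.5, so F(2, 28) is significant in 89% of trials.

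*Linear-time test.* With complete data at 0, 3 and 6 months, the slope weights are −1/6, 0 and +1/6. The 3-month visit has no weight. Dropout gives it a little.

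Probability of significance across the grid, no random slopes:

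| True effect at 3, 6 months | 3-month contrast | Joint 2-df | Linear time |
|---|---|---|---|
| 0, 2 | 5% | 82-92% | 77-90% |
| 2, 0 | 90-92% | 90-92% | 5-9% |
| 2, 2 | 90-92% | 91-94% | 89-93% |
| 0, 0 | 5% | 5% | 5% |

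**Moderate random slopes.** Hold the variance of the 3-month change at 8 and let the SD of the 6-month change rise to 4.0. The (0, 2) row becomes 5% / 68-92% / 43-90%. I go no higher. On a 1-10 scale the largest possible SD is (10 − 1) / 2 = 4.5, and a change SD of 4.5 would imply a 6-month PGSI SD of about 4.4-4.8.

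**Cross-check.** A separate simulation of 30 clusters of 5, with 25% lost by 3 months and a further 10% by 6 months, tested against normal and chi-square references, gave 4.8% / 91% / 89% for (0, 2). For (2, 0) the linear-time test was significant in 6.4%.

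**The case against.** The strongest reply is that the primary comparison is already fixed elsewhere. The analysis paragraph is generic, since it also covers outcomes measured only at baseline and 6 months. The interaction sentence can be read as explaining what the parameter means, not as a rule for declaring success. Read with the outcome section, the relevant interaction for PGSI is the 3-month one. The coding of time and the choice of visits are details that an SAP often carries, and no SAP was available here.

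Much of this stands. The estimand is clear, and two readings remove the mismatch: a model with baseline and 3 months only, or a test of the 3-month coefficient alone. But the text states neither. It does state how a group difference will be inferred, and that statement does not single out 3 months. This is a rule fixed loosely, not a detail left for later.

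The effect patterns in the table are also my choice. The Protocol does not say which pattern it expects. For a sustained effect, without random slopes, the three tests have nearly the same power. The calculation omits the planned adjustment for baseline PGSI, dementia severity and age.

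A reader might infer that the plan inflates the type I error. It does not when there is no effect at either time: each test keeps 5%. A reader might also infer that the groups will be compared only through within-group tests. The Protocol does say that differences in change between groups are assessed by the mixed model; what is missing is the visit. Nor does the Protocol say that an overall interaction would be reported as primary success. The 82-92% becomes a false primary claim only if it is used that way.

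**Conclusion.** The point holds in conditional form. The stated test does not isolate the primary comparison. If all three PGSI visits enter one model, which the text implies but does not state, significance of the overall interaction is not evidence of a 3-month difference. A 6-month effect of 2 points alone would make it significant in 82-92% (joint) or 77-90% (linear) of trials without random slopes, and in 68-92% or 43-90% when moderate slopes are allowed, against 5% for the primary contrast. A linear-time test would find a 3-month effect that fades to zero in only 5-9% of trials.

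The direction follows from the structure of the tests. The sizes rest on the assumed correlation, later loss, 6-month variability, two-sided 5% level and absence of covariate adjustment. It should be fixed because the ambiguity sits on the primary analysis and is cheap to remove. It does not show that the trial is unsound.

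**What to change.** In the quantitative analysis section, state that time is categorical. Name the model-based between-group difference in PGSI change from baseline to 3 months, with its 95% confidence interval and two-sided p-value, as the single primary test. Make the 6-month between-group contrast secondary. State that neither the overall interaction nor the within-group contrasts will be used to claim the primary result.

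This takes two or three sentences and no extra data. If time is already categorical, the fitted model does not change. The price is that a significant overall interaction can no longer support a claim of primary success.
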